a. Medication Randomization. Randomization will be done by the MUSC Investigational Drug Service, who will keep a record of the blind and be available should unblinding be required. Randomization will be stratified on the presence/absence of nicotine use as well as the presence/absence of comorbid anxiety disorders (as these disorders can influence stress reactivity).

b. Micronized progesterone (Prometrium; 200mg): Progesterone is a hormone released mainly during the luteal phase of the menstrual cycle and pregnancy, and has been used for over 50 years in the treatment of various disorders including ovarian failure, premenstrual symptoms, amenorrhea, dysfunctional uterine bleeding, menopausal symptoms and for contraception (de Lignieres, 1999; Simon, 1995). Because it is poorly absorbed and has extensive first pass metabolism, several synthetic progesterone derivatives have been synthesized and marketed. However, these synthetic progesterone derivatives have additional androgenic, corticosteroid and

anabolic effects and have been associated with unfavorable side effects including fluid retention, androgenic effects (e.g., unwanted hair growth and acne) and alterations in lipid profile (Goodman, Gilman, Hardman, Gilman, & Limbird, 1996). Consequently, micronized progesterone formulations that can be taken orally have been developed to overcome the poor absorption of progesterone and the unfavorable side effects of synthetic progesterones (McAuley, Kroboth, & Kroboth, 1996; Simon, 1995). The safety, tolerability and efficacy of micronized progesterone have been demonstrated in multiple studies. Acute effects of micronized progesterone on physiological, performance and subjective measures have been investigated over a wide dose range, from 200 to 2,000 mg/day (Freeman, Rickels, Sondheimer, & Polansky, 1995; Gron, Friess, Herpers, & Rupprecht, 1997; Schweizer, Case, Garcia-Espana, Greenblatt, & Rickels, 1995). Micronized progesterone provides a specific pharmacological tool to investigate the effects of this hormone, devoid of the additional pharmacological effects of synthetic progesterone derivatives.

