Data Management and Reduction: All paper-based assessments (other than laboratory reports) will be entered into REDCap, a secure, web-based application designed exclusively to support data capture for research studies. REDCap provides an intuitive interface for data entry (with data validation), audit trails for tracking data manipulation, and automated export procedures for data downloading to statistical packages such as SPSS and SAS. Quarterly database management and data integrity audits will be conducted.

C.2.d. Statistical Considerations

C.2.d.1. **Statistics and Data Analysis** (complete data analytic plan is provided in Biostatistics Resource Core)

Aim 1: Examine the impact of exogenous progesterone on stress cue reactivity and cannabis craving and withdrawal symptoms during a period of cannabis abstinence in the natural environment.

The primary measures of interest are stress and craving ratings in response to stress-related cues using Cue Reactivity Ecological Momentary Assessment (CREMA) in heavy cannabis using women and men. Hypothesis 1: Compared to placebo, progesterone will attenuate reactivity to stress cues presented in the natural environment among women vs. men with CUD. Hypothesis 2: Compared to placebo, progesterone will attenuate cannabis craving and withdrawal symptoms among women vs. men with CUD. To assess these hypotheses multilevel generalized linear mixed effects models with repeated measures (GLMMs) will be developed using CREMA session response data from the 1-week period during active medication administration. Pre-cue stress and craving rating will be centered and used as a time varying covariate in all analysis. Least squares means and associated standard errors will be used for post-hoc comparisons of cue response and CWS scores between treatment group assignments globally as well as time-specific (AM, PM) treatment group differences. Least squares means and associated standard errors will also be used for post-hoc comparisons of craving and stress response between women and men over time. Relevant interactions will be assessed in the models.

Aim 2: Examine the impact of exogenous progesterone on stress cue reactivity during a laboratory stressor task.

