Following the initial 7-day active exogenous progesterone treatment period, participants will return for a laboratory-based stressor a session. The primary study outcomes of interest in Aim 2 are the differential craving, stress and anxiety responses of progesterone- vs. placebo-treated participants in response to the psychosocial stressor (TSST). Hypothesis 1: Compared to placebo, progesterone will attenuate stress cue reactivity during a human laboratory stress paradigm among women but not men with CUD. Immediately prior to and following the TSST (baseline, +0, +5, +30, and +60 minutes), self-reported measures of stress and craving will be collected. To assess the effect of exogenous progesterone administration on stress and craving response to the TSST, linear mixed effects models will be developed to assess differential treatment responses over time. The primary independent variable of interest will be randomized treatment assignment (progesterone vs. placebo). In addition to overall treatment differences, least squares means and associated standard errors will be used for post-hoc

comparisons between treatment groups at each post-cue time point. Additionally, sex will be added to the model and differential effect of progesterone will be assessed using an interaction term. When significant, stratified treatment effects will be compared and presented across females and males.

Aim 3: Evaluate stress, sex, and endogenous progesterone influences on cannabis craving and use.

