C.2.d.3. Power and Sample Size (complete sample size estimation is provided in Biostatistics Resource Core). In the proposed study, cue response and withdrawal data will be tested using GLMMs (assuming a Gaussian distribution) and the study will be powered to sufficiently address the smallest effect sizes determined to be clinically meaningful for the study hypothesis. Fox and colleagues (2013) examined exogenous progesterone and placebo administration on cue response in 42 cocaine dependent participants. Results indicated that female participants receiving placebo experienced larger negative emotion scores in response to stress-related cues than male participants on placebo ($\Delta=4.7$; $SD_P=3.4$; between sex Cohen's $d > 1.0$, $p < 0.01$). Fox and colleagues also found that administration of exogenous progesterone reduced stress-cue related negative emotions significantly in women ($\Delta=2.4$; $SD_P=3.4$, $d=0.71$) but not in men ($\Delta=-0.7$; $SD_P=3.3$ $d=-0.2$; treatment x sex interaction $\Delta=3.1$; $SD_P=4.7$, $d=0.67$). Assuming a similar response profile between treatment assignments and sex as above, a sample size of 64 participants (32 women, 32 men to each treatment assignment) randomized to the progesterone vs. placebo groups would guarantee 80% power with a type 1 error rate of 5% to detect the least effect size of $d=0.67$ in the stress reduction treatment x sex interaction (total $n=128$) during the 7-day, active treatment CREMA assessment period. Although the proposed study is of relatively short duration, we do anticipate 10% attrition between randomization and the end of the 1-week active treatment period and laboratory session. Thus, inflating the necessary sample size to 70 participants (35 men and 35 women), a total of $n=140$ randomized participants will be needed. Due to app issues at the beginning of the study, some initial data is unusable, so we will randomize 90 men. Additionally, data from our recently completed SCOR project, which examined daily salivary progesterone levels and cigarette smoking behavior for 14 consecutive days in untreated female participants, indicated that increased levels of daily progesterone within participant was associated with decreased cigarettes smoked per day ($\beta=-0.32$; $SE=0.14$; $p < 0.05$). To detect a similar correlation ($\beta=\pm 0.32$; $SD=1.0$) between daily progesterone levels and associated daily use metrics in the proposed study, the randomized sample of 70 women (62 with available follow up data), with 14 days of follow up use data, and with an autocorrelation of 0.9, would provide 80% power. The proposed sample size of **n=160** randomized

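### Randomisation is not stratified by sex although the trial is sized on the treatment-by-sex interaction: no bias and a small loss, cheaply mended by a sex stratum and covariate adjustment

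*Combined protocol and SAP*

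**What the plan says.** C.2.c.3.a (Medication Randomization) names two stratification factors: "Randomization will be stratified on the presence/absence of nicotine use as well as the presence/absence of comorbid anxiety disorders". The reason given is that anxiety disorders can affect stress reactivity. Section C.2.c.3.b repeats that the Investigational Drug Service randomises and adds no factor. Neither section gives a block size or mentions separate lists for women and men.

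The hypotheses concern sex. In C.2.d.1, Aim 1 Hypothesis 1 is that "progesterone will attenuate reactivity to stress cues presented in the natural environment among women vs. men with CUD", and Hypothesis 2 that "progesterone will attenuate cannabis craving and withdrawal symptoms among women vs. men with CUD". The Aim 2 hypothesis is that "progesterone will attenuate stress cue reactivity during a human laboratory stress paradigm among women but not men with CUD"; for its analysis, "sex will be added to the model and differential effect of progesterone will be assessed using an interaction term".

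C.2.d.3 (Power and Sample Size) plans "a sample size of 64 participants (32 women, 32 men to each treatment assignment) randomized to the progesterone vs. placebo groups" to detect a treatment-by-sex interaction of d=0.67. Allowing for 10% attrition, it raises this to 35 women and 35 men per arm. The current target in C.2.a is 70 women and 90 men.

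For Aim 1 the named covariates are pre-cue stress and craving. For Aim 2 the named terms are treatment and sex. Nicotine use and anxiety disorder are not named as covariates. Fuller detail is deferred to the Biostatistics Resource Core, which is not part of the document.

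**The concern.** Recruiting 70 women and 90 men fixes the totals by sex, not the split between arms within a sex. As written, the equal cells used for sizing are assumed rather than produced by the allocation.

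The strata balance anxiety and nicotine use over both sexes together. A surplus of anxious women on progesterone is then offset by a deficit of anxious men on progesterone. The offset cancels in the overall treatment comparison, but the two imbalances add in the difference between the women's effect and the men's effect. At stake is some precision, and the face validity of the within-sex comparisons, for the contrast on which the trial is sized.

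**Working it through.** **Inputs from the documents.** 70 women and 90 men (C.2.a); interaction d=0.67, difference 3.1, SD 4.7, 80% power, 5% type 1 error, 10% attrition (C.2.d.3). Sidedness is not stated; two-sided is used.

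**Assumed inputs.** Anxiety disorder 30%, nicotine use 40%, permuted blocks of 4, and an anxiety effect of 0.5 SD on the outcome. None of these is in the documents.

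**The plan's own figure.** With d=0.67, two-sided 5% and a normal approximation, 32 per cell gives 76.4% power; 80% needs 35 per cell. The stated 32 is therefore not reproduced. That is a separate matter and nothing below depends on it.

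**1. Arm split within women.** If the arms are equal overall (80/80) and sex is ignored, the number of women on progesterone is hypergeometric with SD 3.15 and a 95% range of 29 to 41. With sex as a stratum the simulated range is 33 to 37.

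**2. Power lost to unequal cells.** The interaction variance, in units of the within-cell variance, is the sum of 1/n over the four cells.
- Balanced (35, 35, 45, 45): 2/35 + 2/45 = 0.1016.
- Edge of the 95% range (41, 29, 39, 51): 0.1041, or 2.5% more.
- The within-cell SD is 4.7/√2, so d=0.67 equals 0.67 × √2 = 0.948 within-cell SDs.
- Power = Φ(0.948/√variance − 1.96): 84.4% balanced, 84.2% on average without a sex stratum, 83.6% at the edge. With 10% attrition it is 80.5% balanced and 79.5% at the edge.

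**3. Anxiety imbalance entering the interaction.** This is the between-arm difference in anxiety prevalence in women minus the same difference in men.
- No strata, by formula: √[0.3 × 0.7 × (2/35 + 2/45)] = √(0.21 × 0.1016) = 0.146; by simulation, 0.147.
- Nicotine and anxiety strata, as in the protocol: 0.144.
- Sex added as a third factor: 0.036.

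Multiplied by 1.96, these are about ±29, ±28 and ±7 percentage points. Under the protocol's strata the women's and men's imbalances correlate at −0.93, so those strata control the sum of the two and leave the difference almost untouched. Varying anxiety prevalence from 15% to 50% (nicotine use 40% to 50%) gives ±22 to ±31 points without sex and ±6 to ±8 with it.

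**4. What the imbalance costs.** Set the total outcome variance to 1. Anxiety accounts for 0.5² × 0.21 = 0.0525, leaving 0.9475.
- Current strata: 0.9475 × 0.1016 + 0.25 × 0.144² = 0.1014; standard error 0.3185.
- Sex added: 0.9475 × 0.1016 + 0.25 × 0.036² = 0.0966; standard error 0.3108.
- Reduction: 2.4%.
- Unequal cells add on average (3.15/35)² = 0.8% to the women's variance and (3.15/45)² = 0.5% to the men's. That is about 0.7% overall, or 0.3% in the standard error.
- Together: about 2.7%, or roughly 3%.

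**5. Covariate adjustment instead.** A simulation under the same assumptions gave interaction standard errors of 0.320 without and 0.314 with a sex stratum, a difference of about 2%. With anxiety in the model they were 0.3135 and 0.3134, so the difference disappears.

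**The case against.** The strongest reply is that this is ordinary chance imbalance. The planning SD of 4.7 is an overall SD with no stated reduction for strata or covariates, so variation due to anxiety is already in it. Leaving sex out takes nothing away from the plan; adding it would buy a little precision beyond the plan. This stands.

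Three stronger readings are tempting, and the documents do not support them.
- A reader might infer that the interaction estimate is biased. It is not: allocation is random within each sex whether or not sex is a stratum.
- A reader might infer that the existing strata make matters worse, because the imbalances add. They do not: 0.144 is no larger than the 0.147 under simple randomisation.
- A reader might infer that nothing holds the arms equal within sex. The text shows only that sex is not named. How the pharmacy builds its lists is not described, and neither the Biostatistics Resource Core nor part of the Preliminary Studies section was available.

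Two further replies stand in part. For Aim 2 the primary independent variable is treatment, with sex added afterwards, so the existing strata do serve that overall comparison; the Aim 2 hypothesis is nevertheless sex-specific. Adjustment for pre-cue stress and craving in Aim 1 may absorb some of an anxiety imbalance, but by an unknown amount, and no such adjustment is named for Aim 2.

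**Conclusion.** The point holds as a minor one. The stratification factors do not match the contrast used for sizing, and for that contrast they work hardly better than no strata. The validity of the test is unaffected. The cost is under 1 point of power from unequal cells, even at the edge of the 95% range, and about 3% in the interaction standard error if anxiety shifts the outcome by 0.5 SD. A weaker anxiety effect would cost less.

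The imbalance figures rest on the assumed prevalences and block size, and on allocating all 160 participants under one scheme. The document is Version 16 of June 2022, and C.2.d.3 shows that participants had already been enrolled. The number left to randomise is unknown, so the gain from a new stratum may be smaller than shown. The gain from covariate adjustment does not depend on that number.

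**What to change.** 1. In C.2.c.3.a, add sex to nicotine use and anxiety disorder as a stratification factor for all remaining randomisations (eight strata). If the pharmacy already keeps lists by sex, say so there instead.
2. In the Aim 1 and Aim 2 models (C.2.d.1), include nicotine use and anxiety disorder as covariates alongside sex and treatment-by-sex. This recovers nearly all of the precision and covers those already randomised.
3. Report the number in each arm by sex, with anxiety and nicotine status in each cell.

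The cost is a revised allocation list, two more model terms and one more table; sex is known at enrolment. Eight strata leave a few more incomplete blocks than four. Under the assumed prevalences the smallest stratum of women expects 0.3 × 0.4 × 70, or about 8 participants, so blocks should stay small.
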